#### 4.9 Analysis of Other Groups

When conducting adverse event and efficacy assessments, subgroup analysis shall be performed by considering the items shown below.

If necessary, tests shall be performed on the differences between groups, and in the case of continuous data, analysis shall be performed using a two sample t-test (Wilcoxon's signed rank test if Shapiro-Wilk test results do not satisfy the assumption of normal distribution), while the Pearson's Chi-square test (Fisher's exact test if cells with expected frequency < 5 exceeds 20%) shall be used for categorical data.

- Sex (male, female)
- Age (≤ median, > median)
- Baseline BMI (≤ median, > median)
- Presence or absence of medical history
- Presence or absence of concomitant drugs
- Disease severity (CMTNS-v2) (mild, moderate)

If the subjects within each subgroup are  $\leq$  30%, analysis shall not be performed. For example, if  $\leq$  30% of the total number of subjects is male, no subgroup analysis for sex shall be performed, and whether an analysis should be performed shall be determined in a data review meeting prior to datalock.

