8.1.4 Subgroup Analysis Population

When conducting the adverse events and efficacy assessments, subgroup analysis shall be performed by considering the following items:

- Sex (male, female)
- Age (≤ median, > median)
- Baseline BMI (≤ median, > median)
- Presence or absence of medical history
- · Presence or absence of concomitant drugs
- Disease severity (CMTNS-v2) (mild, moderate)

If there are only a few subjects in each set who correspond to the above subgroup, analysis shall not be performed for the applicable subgroup. For example, if \leq 30% of the total number of subjects is male, no separate analysis for sex shall be performed, and whether a subgroup analysis should be performed shall be determined in a data review meeting prior to datalock.

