#### 1.4 Number of Subjects

#### 1.4.1 Target Number of Subjects and Rationale for Calculation

Using this investigational product, clinical studies have been conducted on six diseases in total since 2007. Although there were no cases in which the drug was applied to CMT1A patients, a total of 18 subjects were recruited in a clinical study on amyotrophic lateral sclerosis among these studies. As a result of assessing safety, it was intended that this clinical study be conducted with 12 subjects considering the addition of indication and the slow progression of disease even though this clinical study also targets similar symptoms.

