#### 4. Statistical Analysis Method

#### 4.1 General Principles of Statistical Analysis

Since this is a phase 1/2a clinical study and the number of subjects is small, the data from the treatment period and the follow-up period shall be descriptively compared and reviewed. For continuous data, descriptive statistics (number of subjects, mean, standard deviation, median, maximum, minimum) shall be presented, while frequencies and percentages shall be presented for categorical data.

If necessary or if comparisons are possible, statistical test shall be performed. The p-value shall be presented up to 4 decimal places, and a two-tailed test shall be performed under a significance level of 0.05. In addition, for descriptive statistics, numbers with values below the decimal point shall be presented up to 2 decimal places.

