#### 4.3 Handling of Dropouts or Missing Values

For missing values due to early termination of subjects, they shall not be imputed and shall be analyzed using the available data set.

Replacements shall be made as shown below if the start date and end date, start date/surgery date, and onset date and recovery date are not collected for prior/concomitant medications (treatment), medical history, and adverse events, respectively. However, if "year" is missing, the date shall not be replaced and shall be handled as a missing value.

Table 1. Handling of missing date values

	Missing	Handling of Missing Value	Exceptions	
Start Date	If only "day" is missing	Replace with 01 (1st day).	If the corresponding date started in the same year and month of Day 0 (first administration day), set it as Day 0.	
	If "day / month" are missing	01 (1st day) / JAN (January)	If the corresponding date started in the same year of Day 0 (first administration day), set it as Day 0.	
	If only "day" is missing	Replace with the last day of the corresponding month	If the end date handled as a missing value falls after the	
End Date	If "day / month" are missing	31 (31st day) / DEC (December)	study termination date or before the study start date, set it as the study termination date.	

Not applicable.

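### SAP 4.9 allows unadjusted between-subgroup tests at 0.05 on up to six factors in 12 subjects, with no criterion for when to test and no exploratory label

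*SAP*

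**What the plan says.** Protocol 8.1.4 plans the subgroups: "When conducting the adverse events and efficacy assessments, subgroup analysis shall be performed by considering the following items". The items are sex, age and baseline BMI (each split at the median), medical history, concomitant drugs, and CMTNS-v2 severity (mild or moderate). It names no test between the levels of a factor. Protocol 8.4.1 sets a descriptive approach because the study is small, but allows statistical testing where it is needed or where comparisons are possible.

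SAP 4.9 repeats the six factors ("subgroup analysis shall be performed by considering the items shown below") and adds: "If necessary, tests shall be performed on the differences between groups". For continuous data, "analysis shall be performed using a two sample t-test". The fallback for non-normal data is the Wilcoxon signed rank test. For categorical data it is Pearson's chi-square test, or Fisher's exact test when expected counts are low.

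The only level stated is in SAP 4.1: "a two-tailed test shall be performed under a significance level of 0.05". The SAP contents list gives section 4.4 to multiplicity. The text standing where that section falls, after the table of missing-date rules, reads "Not applicable".

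Two provisions limit the testing. SAP 2.3 and 4.9 drop a factor when a subgroup holds 30% of subjects or fewer. SAP 2.4 and 4.9 have a data review meeting before datalock settle the planned analyses and decide whether a subgroup analysis is done. On size, SAP 1.4.1 says "it was intended that this clinical study be conducted with 12 subjects".

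**The concern.** The tests compare groups of about 4 to 8 people at an unadjusted 5% level, over several factors and many endpoints. Some nominally significant differences should be expected by chance. The SAP does not call them exploratory, so nothing stops a p-value below 0.05 from being read as a finding, for example that mild patients improved more than moderate ones.

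The necessity condition makes this worse, because no criterion says when it is met. The trial is open-label with one arm (Protocol 5.2), so outcomes may be known to those who choose the tests. Selective testing does not change any single p-value. It changes which p-values get reported, and the reader cannot tell how many comparisons were considered.

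A true difference between levels would also be hard to interpret. With no control arm, a difference in change from baseline cannot separate treatment modification from natural course or regression to the mean. The severity factor is itself defined by CMTNS-v2, which is an efficacy endpoint.

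**Working it through.** The documents state no family-wise error rate, and 12 is justified by comparison with an earlier 18-subject study rather than by a formula. There is therefore no planned figure to reproduce.

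**Inputs from the documents**
- 12 subjects (SAP 1.4.1); 0.05 two-sided per test (SAP 4.1).
- Up to six factors (SAP 4.9). Under the 30% rule 3/12 = 25% is dropped and 4/12 = 33% is kept, so a tested factor is split 4 v 8 or more evenly. Age and BMI are split at the median, so they pass unless ties are heavy. The balance of the other four factors is unknown.
- Continuous endpoint-visits (SAP 4.8): 10MWT at Days 90, 180 and 270 (3), plus MRI fat content, CMAP, SNAP and NCV at Day 270 (4), which makes 7. FDS and ONLS are analysed by the same tests at three visits each, so adding them gives 7 + 6 = 13. CMTNS-v2 items and separate muscles or nerves would add more and are not counted.

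**Assumptions**
- No true subgroup effect.
- Splits unrelated to each other.
- Equal correlation between endpoint-visits of 0, 0.5 or 0.8. The documents give no value.

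**Calculation.** For k independent tests the chance of at least one false difference is 1 - 0.95^k, and 0.05k false differences are expected. With correlated endpoints it was simulated: 12 subjects, 6 v 6 or 4 v 8 splits, pooled two-sample t-tests. Both splits give the same results. Ranges show the spread between simulation runs.

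| Factors x endpoint-visits | Tests k | Expected false | Correlation 0 (formula) | Correlation 0.5 | Correlation 0.8 |
|---|---|---|---|---|---|
| 6 x 1 | 6 | 0.3 | 26% | n/a | n/a |
| 2 x 7 (age, BMI) | 14 | 0.7 | 51% | 42-43% | 28-29% |
| 4 x 7 | 28 | 1.4 | 76% | 65-67% | 49-51% |
| 6 x 7 | 42 | 2.1 | 88% | 80-81% | 63-65% |
| 6 x 13 | 78 | 3.9 | 98% | 92% | 74-75% |

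**Adverse events.** With 12 subjects in a 2 x 2 table, the row with six or fewer subjects always has an expected count below 5, and so does at least one cell of the other row or a second cell of the same row whenever events are neither absent nor universal at 4 v 8 or 5 v 7. At 6 v 6 the two cells of each row sum to 6, so one cell in each row is below 5. More than 20% of cells are then low and Fisher's test applies. Its actual size is at most about 0.7% at 6 v 6 or 4 v 8. At 6 v 6 and a 50% event rate, for example, the rejecting tables carry 26 of 4,096 outcomes, or 0.6%. A 5 v 7 split is less conservative: 88 of 4,096, or 2.1%. Each test stays well below the nominal 5%, so AE tests add little to the table above.

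**Value of the tests.** Power to detect a true 1 SD difference between levels is 35% at 6 v 6 and 32% at 4 v 8. For 0.8 SD it is 24% and 22%. Most real modifiers of that size would be missed.

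**Fallback test.** The Wilcoxon signed rank test needs paired values. The levels of a subgroup factor are independent groups, so the rank-sum test is the matching one.

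**The case against.** The best defence is that SAP 4.9 describes a ceiling. Testing is conditional, the 30% rule can remove factors, and a documented meeting before datalock settles which subgroup analyses are done. A reader might infer that all six factors will be tested on every endpoint, so that a false difference is likely. The documents do not say that. With only the two median splits, the risk on 7 endpoint-visits is about 28-51%.

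A reader might also infer that the SAP contradicts a descriptive-only protocol. It does not: Protocol 8.4.1 already permits tests in general, two-sided at 0.05, and 8.1.4 does not forbid them. SAP 4.9 names specific tests under that permission.

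Nor does any passage use subgroup results to select a later trial population. The protocol synopsis says the study is not intended for efficacy assessment. In a single-arm phase 1/2a safety study, going without family-wise error control is defensible.

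All of this stands and lowers the severity. It does not answer two points. The meeting is given no criterion for the necessity condition, and in an open-label trial it may sit with outcomes already visible. And a descriptive purpose is a reason to label these results exploratory, which the SAP does not do.

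**Conclusion.** The point holds in a limited form. SAP 4.9 permits unadjusted between-subgroup tests on up to six factors in 12 subjects, without a criterion for running them and without an exploratory label. If there is no subgroup effect, the chance of at least one false difference on 7 continuous endpoint-visits is about 28-51% with two factors, about 50-77% with four and about 64-88% with six. Counting FDS and ONLS as well gives about 74-98% with six factors. Even the lowest figure is several times 5%.

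These figures rest on the assumed endpoint correlation of 0 to 0.8, on unrelated splits, and on every test in the stated set being run. How many factors will be tested cannot be known from the documents. The paired fallback test is a plain technical error and does not depend on any of these assumptions.

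Severity is minor to moderate: the analyses are secondary and the primary safety summaries do not depend on them.

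**What to change.** In SAP 4.9, delete the sentence that introduces between-group tests, together with its list of tests. Replace it with wording such as:

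> For each eligible factor, results are summarised by level: number of subjects, mean or median change with 95% confidence interval, or number of subjects with adverse events with exact 95% confidence interval. Subgroup results are exploratory and support no claim of a difference between levels.

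If the sponsor keeps the tests:
- run them for every eligible factor and endpoint, not a selection;
- describe the p-values as nominal and state beside them how many tests were run;
- name the Wilcoxon rank-sum test as the fallback for non-normal data.

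The cost is one paragraph of SAP text. No data or visits change, and Protocol 8.1.4 can stay as it is. What is lost is a set of between-subgroup p-values that carry little information with 12 subjects.

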8.4.4 Secondary Endpoints

(1) Severity of disease

This shall be measured using Charcot-Marie-Tooth Neuropathy Score version 2 (CMTNS-v2) and the functional disability scale (FDS).

: Descriptive statistics (frequency, percentage) for the changes in CMTNS-v2 and FDS at the termination visit (V7) compared with the baseline (V2) shall be presented. A contingency table shall be prepared for the differences before and after administration, and analysis shall be performed using the McNemar's test.

In addition, descriptive statistics (mean, standard deviation, median, minimum, maximum) shall be presented for the changes in FDS at each visit (v4, v6, v7) compared with the baseline (v2), and analysis shall be performed using a paired t-test (wilcoxon signed rank test if the assumption of normal distribution is not satisfied) for the differences at each visit compared with the baseline.

(2) Lower limb function

Changes in lower limb function shall be assessed using the overall neuropathy limitation score (ONLS) and the 10-meter walk test (10MWT).

: Descriptive statistics (mean, standard deviation, median, minimum, maximum) shall be presented for the changes in lower limb function (ONLS leg scale, 10MWT)) at each visit (V4, V6, V7) compared with the baseline (V2), and analysis shall be performed using a paired t-test (Wilcoxon signed rank test if the assumption of normal distribution is not satisfied) for the differences at each visit compared with the baseline.

(3) Degree of Fatty infiltration of lower limb muscles

The muscles of lower limbs shall be imaged with MRI leg scan, and the degree of fatty infiltration of the leg muscles injected with the investigational product shall be measured and evaluated as fat content value (%) at one level for each muscle.

: Descriptive statistics (mean, standard deviation, median, minimum, maximum) shall be presented for the changes in the degree of fatty infiltration of lower limb muscles at the termination visit (V7) compared with the baseline (V2), and analysis shall be performed for the differences before and after administration by using a paired t-test (Wilcoxon signed rank test if the assumption of normal distribution is not satisfied).

(4) Nerve regeneration potential

Nerve conduction studies including compound motor nerve action potential (CMAP), compound sensory nerve action potential (SNAP), and nerve conduction velocity (NCV) shall be performed.

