#### (2) Lower limb function

: Descriptive statistics (number of subjects, mean, standard deviation, median, minimum, maximum) shall be presented for the changes in lower limb function (ONLS leg scale, 10MWT)) at each visit (DAY 90, DAY 180, DAY 270) compared with the baseline (DAY 0), and analysis shall be performed using a paired t-test (Wilcoxon's signed rank test if Shapiro-Wilk test results do not satisfy the assumption of normal distribution) for the differences at each visit compared with the baseline.

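### SAP 4.9 names a paired test, the Wilcoxon signed-rank, as the non-normal fallback for comparing independent subgroups; it should be the rank-sum (Mann-Whitney) test

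*SAP*

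**What the plan says.** SAP 4.9 (Analysis of Other Groups) covers subgroup analyses of adverse events and efficacy. It states the purpose as "If necessary, tests shall be performed on the differences between groups". For continuous data the method is a "two sample t-test (Wilcoxon's signed rank test if Shapiro-Wilk test results do not satisfy the assumption of normal distribution"). Categorical data get a chi-square test, or Fisher's exact test when expected counts are small. The six factors begin with "Sex (male, female") and continue with age and BMI split at the median, medical history, concomitant drugs, and mild or moderate CMTNS-v2 severity. Small subgroups are dropped: in the SAP's own example, if at most "30% of the total number of subjects is male, no subgroup analysis for sex shall be performed".

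The same fallback appears throughout SAP 4.7 and 4.8, but there it is attached to a within-subject test, for example "paired t-test (Wilcoxon's signed rank test if Shapiro-Wilk test results do not satisfy the assumption of normal distribution") for ONLS leg and 10MWT. Protocol 8.4.4 does likewise: "wilcoxon signed rank test if the assumption of normal distribution is not satisfied", again as the alternative to a paired t-test. Protocol 8.1.4 lists the subgroups but names no between-group test. Neither document mentions a rank-sum or Mann-Whitney test.

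**The concern.** The two tests named in 4.9 belong to different designs. A two-sample t-test compares two independent sets of subjects. A signed-rank test ranks the absolute values of differences within pairs, or of one sample of changes, and asks whether they centre on zero. Men and women, or mild and moderate patients, are not pairs. The counterpart of the two-sample t-test is the rank-sum test. The parenthesis matches the wording in 4.8, which suggests it was carried over from the within-subject analyses, though the documents do not confirm this.

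At stake is whether the fallback p-values mean anything. Whoever programs 4.9 must either depart from the SAP, choosing the replacement once data are in hand, or report a p-value that does not address the subgroup difference.

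**Working it through.** The plan gives no power, error rate or effect size for these comparisons, so there is no figure to reproduce. The check asks what happens if the text is followed.

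**Inputs.** Sample size: "it was intended that this clinical study be conducted with 12 subjects" (SAP 1.4.1). Level: "a two-tailed test shall be performed under a significance level of 0.05" (SAP 4.1). Subgroups holding 30% or less of subjects are not analysed (SAP 2.3 and 4.9).

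**Step 1, admissible splits.** 0.30 × 12 = 3.6, so the smaller subgroup needs at least 4 subjects. The splits are 4/8, 5/7 and 6/6.

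**Step 2, reading A: signed-rank on the two groups as if paired.**
- At 4/8 and 5/7 the samples differ in length. No pairing exists and the software call returns an error.
- At 6/6 the call runs, but it pairs subjects by their order in the file. Take the illustrative values −2.1, −1.3, −0.4, 0.2, 0.9, 1.6 against −0.73, 0.11, 0.85, 1.44, 2.37, 3.12. Over all 6! = 720 pairings the exact two-sided p runs from 0.031 to 1.00. The exact rank-sum p is a single value, 0.240.
- A median split of 12 subjects gives 6/6 unless values tie at the median. So age and BMI are where this would run without warning.

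**Step 3, reading B: signed-rank on the pooled 12 changes.** This tests change from baseline. Simulation used 4,000 runs per setting, normal changes with SD 1, and the same shift in both groups, so there is no subgroup difference. The shifts are assumptions, because the documents give no expected change or SD.

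| Common shift (SD) | Pooled signed-rank rejects |
|---|---|
| 0 | about 4% |
| 0.2 | about 9% |
| 0.3 | about 13% |
| 0.5 | about 31% |
| 1.0 | about 85% |

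The rank-sum test stayed at about 4% to 5% throughout. With opposite shifts of +1 and −1 SD, a large true difference, pooled signed-rank rejected 0.5% (6/6) and 3.9% (4/8), against 83% and 80% for rank-sum. The pooled version can therefore create a subgroup finding or hide one.

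**Step 4, reading C: signed-rank within one subgroup.** The smallest two-sided p without ties is 2/2ⁿ: 0.125 at n = 4, 0.0625 at n = 5 and 0.031 at n = 6. In a subgroup of 4 or 5 it cannot reach 0.05.

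**Step 5, the rank-sum test.** It is defined at every split. Its smallest two-sided p without ties is 2/C(12, k):
- 4/8: 2/495 = 0.0040
- 5/7: 2/792 = 0.0025
- 6/6: 2/924 = 0.0022

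**Step 6, how often the fallback applies.** FDS is an integer scale from 0 to 8. For 12 changes limited to −1, 0 and +1, Shapiro-Wilk rejected in essentially every simulated sample. Tested separately in two groups of six, at least one group failed (or was constant) in roughly 77% to 91% of samples, depending on the assumed distribution. SAP 4.9 does not say which of these two ways normality is to be checked. For continuous measures the fallback is rarer: at six per group, about 5% rejection for normal data, 12% for t with 3 degrees of freedom and 21% for exponential data.

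**The case against.** No one can defend the wording itself; the case on the other side is about weight. The tests are run only if judged necessary, only for continuous data, only when normality is rejected, and only for subgroups that pass the 30% rule and the data review meeting. The study is a 12-subject phase 1/2a trial with a safety primary objective and a descriptive general approach, and no decision rule uses a subgroup p-value. At unequal splits the error shows itself as a failed call, and the stated aim makes the intended test easy to guess. The 85% figure comes from one large assumed shift under an analysis that the SAP does not literally describe. With heavily tied scores, even the right test may have no room: if 4 of 12 subjects change by one point and 8 do not change, the smallest two-sided p at 6/6 is 2 × 15/495 = 0.061 for rank-sum and 2/2⁴ = 0.125 for pooled signed-rank.

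Most of this stands as a limit on reach. The pooled result should be read over its whole range, about 4% to 85%, and the tie example shows that rank-sum will not make subgroup tests informative on coarse scales. Two points do not stand. The error is not always visible, because equal splits, the expected result for age and BMI, run silently. And an easily guessed intention is no substitute for a pre-specified test, since the SAP is the only document that gives the method.

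**Conclusion.** The concern holds. As written, the non-normal fallback in SAP 4.9 either cannot be computed (4/8 and 5/7) or answers another question: an arbitrary pairing at 6/6, or change from baseline if pooled. The mismatch follows from the design and needs no assumption. The simulated rates depend on assumed normal changes and shifts and serve only as illustration. The 720-pairing range shows that the result is arbitrary; it does not estimate an effect in this trial.

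The error is confined to the continuous-data fallback of optional subgroup comparisons. The primary safety analysis, the within-subject tests in SAP 4.7 and 4.8, the two-sample t-test and the chi-square/Fisher branch are unaffected. Within that scope the specified test is wrong and should be corrected before the analysis is run.

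**What to change.** In SAP 4.9, replace the signed-rank test with the exact Wilcoxon rank-sum (Mann-Whitney) test, using an exact version that allows for ties. Keep signed-rank in SAP 4.7 and 4.8 and in Protocol 8.4.4, where it is the correct partner of the paired t-test. The protocol needs no change, since 8.1.4 names no between-group test. The cost is a few words in the SAP and one procedure call; no additional data are needed and no other analysis changes.

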5.3 Subjects

5.3.1 Target Number of Subjects and Rationale for Calculation

Using this investigational product, clinical studies have been conducted on six diseases in total since 2007 (see Table 2). Although there were no cases in which the drug was applied to CMT1A patients, a total of 18 subjects were recruited in a clinical study on amyotrophic lateral sclerosis (see section 3.8.5) among these studies. As a result of assessing safety, it is intended that this clinical study be conducted with 12 subjects, which is set less than the size of subjects in the study of amyotrophic lateral sclerosis because it is just addition

of the indication and the progression of CMT1A is slow although this clinical study also targets similar symptoms.

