#### 1.3 Clinical Study Subjects

#### 1.3.1 Inclusion Criteria

Subjects enrolled in this clinical study must satisfy all of the following inclusion criteria:

- Males and females ≥ 19 years of age and ≤ 65 years of age
- Patients with confirmed diagnosis of CMT1A by genetic testing
- Patients with mild-to-moderate severity assessed by Charcot-Marie-Tooth Neuropathy Score version 2 (CMTNS-v2) with a score > 2 and ≤ 20
- 4) Individuals with lower limb muscle weakness with minimum dorsiflexion or more
- Individuals who voluntarily consented to participate in this study and signed the IRB-approved informed consent form after listening to a description on the characteristics of this clinical study prior to all screening tests
- 6) Individuals who can comply with the requirements in the clinical study
- In case of females of child-bearing potential, those who test negative in a urine or serum pregnancy test at screening
- 8) Individuals who practice medically approved contraceptive methods\* throughout the clinical study

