#### 2.3 Subgroup Analysis Population

When conducting assesments for adverse event and efficacy subgroup analysis shall be performed by considering the following items:

- Sex (male, female)
- Age (≤ median, > median)
- Baseline BMI (≤ median, > median)
- Presence or absence of medical history
- Presence or absence of concomitant drugs
- Disease severity (CMTNS-v2) (mild, moderate)

If the subjects within each subgroup are  $\leq$  30%, analysis shall not be performed. For example, if  $\leq$  30% of the total number of subjects is male, no subgroup analysis for sex shall be performed, and whether an analysis should be performed shall be determined in a data review meeting prior to datalock.

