#### CMTNS-v2

Charcot-Marie-Tooth Neuropathy Score version 2 (CMTNS-v2) is a measurement tool for evaluating the severity of disease. Measurements shall be taken for 9 items which include 3 items for disease symptoms, 4 items for signs, and 2 items for neurophysiological testing. The severity of disease shall be classified according to scores as mild (≤10), moderate (11 to 20), and severe (>20). This clinical study shall target mild to moderate patients. This was performed at Visit 1 (screening), Visit 2 (Day 0), and Visit 7 (termination visit, Day 270) (performed prior to administration at Visit 2 [Day 0]).

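### SAP 4.9 examines age, baseline BMI and CMTNS-v2 severity only as two-group cuts; with 12 subjects, any exploratory test of these factors would tell more if it used the recorded values

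*SAP*

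**What the plan says.** SAP 4.9 names six subgroup factors for the adverse event and efficacy assessments. Three of them are numbers at source: "Age (≤ median, > median"), "Baseline BMI (≤ median, > median") and "Disease severity (CMTNS-v2) (mild, moderate"). SAP 2.3 and protocol 8.1.4 carry the same list.

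The first two are cut at the sample median. Severity is cut at a fixed clinical boundary defined in SAP 3.3: "The severity of disease shall be classified according to scores as mild (≤10), moderate (11 to 20), and severe (>20"). Eligibility requires "CMTNS-v2) with a score > 2 and ≤ 20", so only the mild and moderate bands can occur. No mix of the two is targeted.

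Tests of the difference between groups are conditional on being judged necessary. If they are run, "in the case of continuous data, analysis shall be performed using a two sample t-test"; categorical data get Pearson's chi-square, or Fisher's exact test when more than 20% of cells have an expected count below 5. SAP 4.1 sets the level: "a two-tailed test shall be performed under a significance level of 0.05". A subgroup holding 30% or less of the subjects is not analysed, and the data review meeting before datalock decides whether an analysis is performed.

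No section analyses age, BMI or the score on its own scale. SAP 4.2 lists covariate adjustment as not applicable.

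**The concern.** Cutting a measured value in two treats everyone on one side as identical. On the severity factor, scores of 3 and 10 count as the same while 10 and 11 count as different. With 12 subjects there is little information to begin with, and the cut discards part of it for no stated reason. For age and BMI the boundary is also set by these particular 12 people, so the groups formed here cannot be reproduced in a later study.

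At stake is how much the exploratory results can say about whether change scores or adverse events vary with age, BMI or baseline severity. Safety and tolerability are the primary objective, and SAP 4.9 applies these subgroups to adverse events too. For severity there is a further consequence: the 30% rule can remove the analysis, although the score itself needs no minimum group size.

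**Working it through.** **Inputs.** N = 12 (protocol 5.3.1: "it is intended that this clinical study be conducted with 12 subjects"); two-sided 0.05 (SAP 4.1); cuts, tests and 30% rule (SAP 4.9); mild ≤10, moderate 11 to 20 (SAP 3.3). There is no planned power figure to reproduce: the 12 rests on comparison with an 18-subject study in amyotrophic lateral sclerosis, and no effect size, SD or severity mix is given. Correlations, event risks and severity mixes below are therefore assumptions, shown as ranges.

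**1. Continuous outcome, median split v actual value.** Simulation with n=12, normal factor and outcome with true correlation ρ, 100,000 trials per setting. Split: two-sample t-test, 6 v 6, 10 df. Uncut: t = r√[(n−2)/(1−r²)], also 10 df. At ρ=0 all tests reject about 5% of the time.

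| ρ | Slope (Pearson) | Spearman | Median split | Loss v slope | Loss v Spearman |
|---|---|---|---|---|---|
| 0.2 | 9.4% | 8.9% | 7.5% | 2 | 1 |
| 0.3 | 15.7% | 14.3% | 11.2% | 5 | 3 |
| 0.4 | 25.7% | 22.5% | 16.7% | 9 | 6 |
| 0.5 | 40.0% | 33.9% | 24.3% | 16 | 10 |
| 0.6 | 58.4% | 50.1% | 35.2% | 23 | 15 |
| 0.7 | 77.9% | 68.3% | 49.7% | 28 | 19 |
| 0.8 | 93.2% | 86.4% | 67.9% | 25 | 19 |

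Losses are in percentage points. As a cross-check, a median split of a normal variable shrinks the correlation by √(2/π) ≈ 0.80. So ρ=0.7 acts like 0.56, and the 49.7% falls between the slope's 40.0% at 0.5 and 58.4% at 0.6, as it should. With a uniform factor the largest loss against the slope is 23 points, also at ρ=0.7.

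**2. Severity cut.** This is a fixed boundary, so the groups need not be equal. At ρ=0.7 the t-test has 49.6% power for 6/6, 48.5% for 5/7 and 45.2% for 4/8.

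**3. Adverse events (event yes/no per subject).** The four expected counts in a 2×2 table sum to 12. Three counts of 5 or more would need at least 15, so at least two of the four cells are always below 5. That is 50%, above the 20% trigger, and Fisher's test always applies.

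On a 6 v 6 split:
- 5 v 0: p = 2×6/792 = 0.015. By symmetry 6 v 1 gives the same. 6 v 0: p = 2/924 = 0.002.
- 4 v 0: p = 2×15/495 = 0.061.
- 5 v 1: p = 2×(36+1)/924 = 0.080.

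Only 5-0, 6-0, 6-1 and their mirror images reach p<0.05, so an event seen in 4 or fewer subjects can never do so. At 50% risk and no association, the chance of rejecting is 2×(6+1+6)/4096 = 26/4096 = 0.6%. An exact rank-sum test of the factor between subjects with and without the event can reach 2/66 = 0.030 with only 2 events. With 1 event its smallest p is 2/12 = 0.17.

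This result depends on an exact 6/6 split. A tie at the median can give 7 v 5, where 3 events all in the smaller group give C(5,3)/C(12,3) = 10/220 = 0.045.

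How much of the gap comes from the cut? Power at 50% average risk, by log-odds slope per SD of the factor:

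| Slope | Fisher, split | Mid-p Fisher, split | Exact rank-sum, uncut |
|---|---|---|---|
| 1 | 5% | 17% | 24% |
| 1.5 | 10% | 29% | 42% |
| 2 | 15% | 40% | 58% |
| 3 | 27% | 57% | 78% |

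At slope 2 the total gap is 58−15 = 43 points. Of these, 40−15 = 25 disappear when the same split is tested less conservatively, leaving 18 for the cut.

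**4. The 30% rule and severity.** 0.30×12 = 3.6, so a band with 3 or fewer subjects triggers it. With X the number of mild subjects, the chance is P(X≤3) + P(X≥9), binomial with n=12. For an even mix it is 2×(1+12+66+220)/4096 = 598/4096 = 14.6%. For 40/60 it is 24.1%, for 30/70 49.4% and for 20/80 79.5%.

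**The case against.** The strongest reply is that this is an optional, exploratory analysis in a single-arm trial whose primary objective is safety. SAP 4.1 makes the comparisons descriptive because the sample is small, and SAP 4.9 tests subgroup differences only where judged necessary. The core output is the grouped tables, which nobody proposes to remove. Both methods have low power at modest correlations. A slope in a single-arm trial cannot separate treatment response from natural progression, and at n=12 one extreme subject can pull it. For uncommon events the rank-sum test is weak too: at 10% risk its power is only about 5 to 20% over the slopes above. All of this stands, and it limits the consequence. It does not favour the cut: a test run only when needed should still use the information on hand.

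Several stronger readings are tempting but not supported:
- *A loss of 10 to 28 points as a general fact.* A loss of that order needs a true correlation of roughly 0.4 to 0.8, which no section gives.
- *The severity analysis will often be cancelled.* The mix is not stated, and the chance runs from 15% to 79% across the mixes assumed above. Protocol 5.7.1 says enrolment is complete, so the mix can be counted, and the data review meeting has the final say.
- *The whole adverse event gap is due to the cut.* In the scenario above more than half of it is Fisher's conservatism.
- *Severity is another arbitrary 6 v 6 median split.* It is a fixed clinical band that a later study can reproduce.
- *These are the only planned looks at who improves.* Protocol 8.4.4 and SAP 3.3 also plan a preliminary comparison of antibody production between improved and non-improved subjects.

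**Conclusion.** The point holds as a low-cost improvement to an exploratory analysis. It is not an error that threatens the trial's main results. The plan cuts three recorded numbers in two and never analyses them uncut.

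For continuous outcomes the cost is 9 to 28 points of power against a slope, and 6 to 19 against Spearman, if the true correlation is 0.4 to 0.8. At 0.2 to 0.3 it is 2 to 5 points and of little practical weight. These figures assume 12 evaluable subjects, a normally distributed factor and a linear trend.

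For adverse events, the blindness of Fisher's test to events in 4 or fewer subjects needs no assumed effect size, but it does need an exact 6/6 split. Only part of it is attributable to the cut. The 30% rule can cancel the severity analysis; how likely that is depends on a mix the documents do not state.

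**What to change.** In SAP 4.9 and 2.3, and in protocol 8.1.4 for consistency:

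- Keep the ≤/> median and mild/moderate tables as descriptive displays.
- Where a test is judged necessary for age, BMI or severity, use the recorded age, the recorded BMI or the Day 0 CMTNS-v2 total. For continuous outcomes, show a scatter plot with the regression slope and 95% CI, or Spearman's correlation if the residuals are clearly non-normal. For adverse events, use an exact rank-sum test of the factor between subjects with and without the event.
- Do not apply the 30% rule to these full-scale analyses.
- When the outcome is the CMTNS-v2 change, keep severity descriptive, because change and baseline share the same measurement.
- Label all of this exploratory, and say that a single-arm slope cannot distinguish treatment response from natural progression.

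The cost is a few lines of text and programming, with no new data and no change to conduct. The downside is the leverage of a single extreme subject at n=12, which is why the scatter plot should accompany every slope.

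A separate correction belongs in the same paragraph of SAP 4.9: the fallback named for two independent groups is a rank test for paired data.
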